#### **Safety Population**

Any participant who receives the study medication will be included for the analyses of adverse events.

### **10.3 Variables and Planned Statistical Analyses**

#### **Variables**

##### **Primary Variable**

- Agreement (strongly agree or somewhat agree) of perception of cooling sensation based on a 5 point agreement scale

Adverse events will be collected and assessed by the investigator.

#### **Statistical and Analytical Plans**

**Questionnaire:** The primary variable of interest will be analyzed by determining the percentage of selection of the top 2 choices (strongly agree and somewhat agree). This percentage and its 95% confidence interval will be calculated, if the lower bound of the confidence interval is greater than 50%, the statistical majority of agreement will be claimed. Other secondary variables of interests from the questionnaire will be analyzed in the same manner as the primary variable.

**Time to perception of cooling and duration of cooling:** These secondary variables will be analyzed descriptively (Mean, Standard deviation, Median, Mode and Range). The mean time point at which cooling is initially perceived will be claimed as the onset of cooling. The mean time point at which cooling is perceived to last will be claimed as the duration of cooling.

Participants who never reach “Yes” in the perception of cooling will be (1) imputed by the maximum study time (60 minutes), and (2) treated as censored and used Kaplan-Meyer to estimate the median time to perception of cooling.

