	
 
• Participant will be asked to indicate if he/she perceives a cooling sensation in each of the locations (mouth, nose and throat) at 10 seconds, 30 seconds and 1 minutes post ingestion of study product
 
• After the 1 minute time point, participants will be asked to complete a brief questionnaire on the sensory attributes of the test product. Participants will be allowed four (4) minutes to complete the questionnaire.
 
• Following the completion of the questionnaire, participants will continue to evaluate perception of cooling sensation in the mouth, nose and throat starting at the 5 minute time point and at 5 minute intervals for 60 minutes
 
• Following completion of all study assessments, participants will be asked open ended questions which will be used for learning purposes
 
• The study visit will last approximately 60-75 minutes.
 
• Adverse events, if applicable, will be recorded
 
• Participants will be reminded to report any unusual or unexpected medical changes within the 24 hour period following administration of the study product to site personnel
 
 
Follow Up Phase
 
 
• At the End of Study, if a participant has an ongoing adverse event, the adverse event will be monitored and recorded and the participant will be contacted during the following week after discharge from the study site.
 

Number of Participants	Approximately 400 adults (100 per location: North East, South, Midwest and West regions within the United States of America)
Primary Variable	
 
• Agreement (strongly agree or somewhat agree) of perception of cooling sensation based on a 5 point agreement scale
 

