Plan for Statistical Analysis	
Sensory attributes questionnaire: The percentage of selection of the top 2 choices (strongly agree and somewhat agree) will be determined for each question. This percentage and its 95% confidence interval will be calculated, if the lower bound of the confidence interval is greater than 50%, the statistical majority of agreement will be claimed.
 
Time to perception of cooling and duration of cooling: variables will be analyzed descriptively (Mean, Standard deviation, Median, Mode and Range). The mean time point at which cooling is initially perceived will be claimed as the onset of cooling. The mean time point at which cooling is perceived to last will be claimed as the duration of cooling. Participants who never reach “Yes” in the perception of cooling will be (1) imputed by the maximum study time (60 minutes), and (2) treated as censored and used Kaplan-Meyer to estimate the median time to perception of cooling.

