## 4. STUDY OBJECTIVES

### Primary Objective

- To evaluate perception of cooling sensation of a single dose flavored chewable antihistamine tablet

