**9.4.2 Sensory Attributes Questionnaire**

Participants will be instructed to complete the questionnaire as following:

“Please indicate to what level you agree or disagree with the corresponding statement:”

Question	Strongly agree (5)	Somewhat agree (4)	Neither agree nor disagree (3)	Somewhat disagree (2)	Strongly disagree (1)
The product provides a cooling sensation					
The product provides a cooling sensation in the mouth					
The product provides a cooling sensation in the nose					
The product provides a cooling sensation in the throat					
The product provides a refreshing sensation					
The product provides a refreshing sensation in the mouth					
The product provides a refreshing sensation in the nose					
The product provides a refreshing sensation in the throat					
The product tastes great					
The product experience was enjoyable					

I like the flavor sensation of the product					
The product feels soothing on the throat					
The sensory experience is unique for an allergy medicine					
The cooling sensation is refreshing					

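### Do the other 13 questionnaire items need a multiplicity rule or a supportive label because they share the primary's majority-claim rule?

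*Combined protocol and SAP*

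**What the plan says.** Section 10.3 names one primary variable: "Agreement (strongly agree or somewhat agree) of perception of cooling sensation based on a 5 point agreement scale". Section 4 has one objective, also primary: "To evaluate perception of cooling sensation of a single dose flavored chewable antihistamine tablet".

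The analysis text in Section 10.3 takes the share choosing the top two answers. "This percentage and its 95% confidence interval will be calculated", and "if the lower bound of the confidence interval is greater than 50%, the statistical majority of agreement will be claimed" (the synopsis uses the same words). The other items are covered in one sentence: "Other secondary variables of interests from the questionnaire will be analyzed in the same manner as the primary variable".

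The synopsis makes no split between primary and secondary: "The percentage of selection of the top 2 choices (strongly agree and somewhat agree) will be determined for each question". Section 9.4.2 lists 14 statements, from general cooling through taste and enjoyment to items such as "The sensory experience is unique for an allergy medicine".

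The secondary items are not listed one by one under Variables in Section 10.3. The plan does not say whether a majority claim on them is supportive, and it does not mention multiplicity.

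**The concern.** The word used is that a majority will be claimed. This is a pass/fail rule on a confidence bound, and it applies in the same terms to the primary variable and to every other item. By contrast, Section 10.3 analyses time to cooling and its duration descriptively. It is therefore not obvious that the other items are meant only as description.

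If the first item (general cooling, no body site named) is the primary, 13 further claims are possible, each at a one-sided level near 2.5%. The chance that at least one is false can exceed 2.5%, and the plan neither controls nor discloses this. A reader shown several majority claims, on taste or uniqueness for instance, might give them all the standing of the primary result. At stake would be the credibility of the secondary statements, not the primary conclusion.

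**Working it through.** **Inputs.** The sample size is 400 (Section 10.4), assumed complete for every item. The null value is 50% and the interval is 95% (Section 10.3), read as two-sided. The interval method is not named, so Wald, Wilson and exact are all tried. There are 14 items (Section 9.4.2), which leaves 14 − 1 = 13 if the first is the primary. The documents give no expected agreement and no correlation between items, so ranges are shown. The plan states no power or error figure to reproduce.

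**Cut-off.** This is the smallest count whose lower 95% bound exceeds 50%:
- Wald: 220/400 = 55.0%. Lower bound 0.55 − 1.96 × √(0.55 × 0.45/400) = 0.5012.
- Wilson: 220/400.
- Exact (Clopper-Pearson): 221/400 = 55.25%.

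**Error of one item.** This is the binomial probability P(X ≥ cut) with n = 400:

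| True agreement | Cut 220 | Cut 221 |
|---|---|---|
| 50% | 0.0255 | 0.0201 |
| 49% | 0.0094 | 0.0071 |
| 48% | 0.0030 | 0.0022 |
| 47% | 0.0008 | 0.0006 |

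Each claim, the primary included, holds its own level.

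**Thirteen items together.** If they were independent and all at 50%, the chance of at least one false claim would be 1 − (1 − 0.0255)^13 = 28.5% at cut 220, or 1 − (1 − 0.0201)^13 = 23.2% at cut 221. Independence is not credible, because the same people rate overlapping statements in one short sitting: "Participants will be allowed four (4) minutes to complete the questionnaire". Simulating yes/no answers from equally correlated latent normal variables gives:

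| Latent correlation | All at 50%, cut 220 | All at 50%, cut 221 | All at 49%, cut 220 | All at 48%, cut 220 |
|---|---|---|---|---|
| 0.5 | 21% | 18% | 9% | 3% |
| 0.7 | 17% | 14–15% | 7% | 3% |
| 0.9 | 11–12% | 10% | 5% | 2% |
| 0.988 | 7% | 5–6% | 3% | 1% |

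At a true 50%, these latent values correspond to correlations between the yes/no answers of (2/π) × arcsin(ρ) = 0.33, 0.49, 0.71 and 0.90. If all items are at 47%, the chance is under 1%.

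If only some items are at 50% and the rest are well above, at latent correlation 0.9 to 0.5 and cut 220, the chance is about 2.5% for one item, 6–7% for three and 8–12% for six. The excess over 2.5% therefore needs several items within about one or two points of 50%. A false claim there would misstate true agreement by about that much.

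**What a remedy would change.** Labelling the 13 items supportive and unadjusted leaves the cut at 220–221 and changes no interval or power. Formal adjustment does have a cost. The table shows the power of one item at its strictest step (the range covers the interval methods):

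| Rule | Cut | True 57% | True 60% |
|---|---|---|---|
| As planned | 220–221 | 78–80% | 98% |
| Holm, three key items | 224–225 | 64–68% | 94–95% |
| Holm, all 13 items | 229–230 | 44–48% | 86–88% |

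A fixed testing order would keep the cut at 220–221, but one failure would block every later claim.

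**The case for a change.** The strongest case for acting is that the gap is real and cheap to close. The plan sets a claim rule rather than a description, the synopsis gives all 14 questions equal standing, and one sentence would tell readers that 13 of the claims are supportive and unadjusted. Committing to report every item would also guard against showing only the favourable ones. In addition, the primary variable is not tied to a numbered item. Items 2 to 4 also ask about cooling, by site, and if they counted as primary, 10 others would remain instead of 13.

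Part of this stands. The plan does not state the status of the secondary claims, and the count of 13 rests on taking the first item as the primary.

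The rest is already met or makes no difference. Section 10.3 separates the primary variable from the other questionnaire variables and calls those secondary as a class. The synopsis plans a percentage for each question, so results on every item are due whether or not the rule is met. The first item is the only cooling statement that names no body site, as the primary variable names none, so an analyst would take it as the primary. The missing words would therefore record how the results would be read anyway.

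**Conclusion.** No change to the plan is needed. The omission is one that analysts and readers fill sensibly: one primary variable, and pre-specified secondary items each shown with its own unadjusted 95% interval. The primary test is unaffected, and each item's error is 2.0% to 2.6% at a true 50%.

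The worst-case chance of a false claim somewhere among 13 items, about 5% to 21%, requires every item to sit at exactly 50%. It falls to about 2% to 9% if all are at 49%, and to about 3% or less at 48% or below. Formal control is a trade-off that the sponsor may reasonably decline in a single-arm sensory study of a marketed tablet, which Section 9.5.8 says is not designed to assess efficacy.

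These figures assume 400 complete responses per item, the first item as the primary, equal correlation between items and latent correlations from 0.5 to 0.988. The documents give no expected agreement or correlation, so the true risk cannot be narrowed further. The conclusion does not depend on where it falls, because a label would change no result at any point in the range.

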#### **6.4.2 Participant Discontinuation/Withdrawal from the Study**

- A participant may withdraw from the study at any time at his/her own request, or at the request of their legally acceptable representative, or may be withdrawn at any time at the discretion of the investigator for safety, behavioral, compliance, or administrative reasons.
- A participant may be withdrawn from the study at the specific request of the sponsor and in liaison with the investigator (e.g. obvious non-compliance, safety concerns).
- At the time of discontinuing from the study, if possible, an early discontinuation visit should be conducted, as shown in the Schedule of Activities (SoA). See SoA for data to be collected at the time of study discontinuation and follow-up and for any further evaluations that need to be completed.
- The participant will be permanently discontinued both from the study intervention and from the study at that time.
- If the participant withdraws consent for disclosure of future information, the sponsor may retain and continue to use any data collected before such a withdrawal of consent.

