#### 9.4.1 Cooling Time Point Assessment

Participants will be instructed to complete as follows:

“Please indicate at each time point whether you perceive a cooling sensation in the mouth (1), nose (2), throat (3) or (4) No Sensation Felt.

Time	Cooling in the mouth (1)	Cooling in the nose (2)	Cooling in the throat (3)	No Sensation Felt (4)
Immediate (10 seconds)				
30 seconds				
1 minute				
Complete the sensory attributes questionnaire (see questionnaire below)				
5 minutes				
10 minutes				
15 minutes				
20 minutes				
25 minutes				
30 minutes				
35 minutes				
40 minutes				
45 minutes				
50 minutes				
55 minutes				
60 minutes				

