## **10. STATISTICAL METHODS AND DETERMINATION OF SAMPLE SIZE**

### **10.1 General Considerations**

All statistical analyses will be conducted using SAS. Missing data will not be imputed.

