### 11.5 Missing Data

Any missing data will be left as such.

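### The claimed onset of cooling is a mean in which, on the natural reading, participants who never feel cooling count as 60 minutes

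*Combined protocol and SAP*

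**What the plan says.** Section 10.3 (Statistical and Analytical Plans) and the synopsis (Plan for Statistical Analysis) treat time to cooling in the same way. Mean, standard deviation, median, mode and range are to be reported, and one of them carries the claim: "The mean time point at which cooling is initially perceived will be claimed as the onset of cooling".

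Participants who never report cooling are then handled by two numbered rules. They are "imputed by the maximum study time (60 minutes), and (2) treated as censored". The second rule has a named use: the plan "used Kaplan-Meyer to estimate the median time to perception of cooling". The first rule is tied to no statistic. Both sit in a paragraph that covers duration of cooling as well as onset.

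The data come from the grid in Section 9.4.1, where participants indicate at each time point "whether you perceive a cooling sensation in the mouth (1), nose (2), throat (3) or (4) No Sensation Felt". The time points are 10 seconds, 30 seconds, 1 minute, and then every 5 minutes to 60. Section 10.3 does not say whether first perception means any location or each location. The synopsis (Methodology) has participants answer for mouth, nose and throat one by one.

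**The concern.** A participant who marks no cooling up to 60 minutes has no onset time. Giving that person the value 60 counts never having felt cooling as having first felt it at the last assessment. With possible onset values starting at 10 seconds, a few values of 60 can dominate an average, so the claimed figure may say more about how many people felt nothing than about how fast the others felt something.

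Leaving the 60-minute values out does not rescue the mean. A perceivers-only mean is the same whether 1% or 40% feel nothing. Neither version is a sound single figure for onset, and this is the figure the sponsor intends to claim.

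**Working it through.** **Which statistic the 60-minute value feeds.** Rule (2) is assigned to the Kaplan-Meier median. The natural use left for rule (1) is the descriptive statistics, and so the mean. The alternative is to read the two rules together as one Kaplan-Meier set-up (time 60 with a censoring flag). That is possible, but it sets aside the separate numbering.

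**Inputs from the documents.** Imputed value: 60 minutes (10.3). Earliest recordable onset: 10 seconds, or 1/6 minute (9.4.1). Planned sample: 400 (10.4). The plan states no onset figure, so there is nothing of its own to reproduce.

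**Assumed inputs.** Let q be the share who never perceive cooling and m the perceivers' mean onset in minutes. The documents give neither. I use q = 1% and 5% (4 and 20 people of 400) and m from 10 seconds to 5 minutes.

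**Formulas.**
- Claimed mean with imputation: M = (1 - q) × m + 60q
- Share of M supplied by the imputed values: 60q / M
- Shift from the perceivers-only mean: M - m = q × (60 - m)

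Example, q = 5% and m = 1: M = 0.95 × 1 + 60 × 0.05 = 0.95 + 3.00 = 3.95 min; share = 3.00 / 3.95 = 75.9%; shift = 0.05 × 59 = 2.95 min.

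| m (perceivers-only mean) | q | M (min) | Share from imputed values | Shift (min) |
|---|---|---|---|---|
| 10 s | 1% | 0.765 | 78.4% | 0.60 |
| 10 s | 5% | 3.158 | 95.0% | 2.99 |
| 30 s | 1% | 1.095 | 54.8% | 0.60 |
| 30 s | 5% | 3.475 | 86.3% | 2.98 |
| 1 min | 1% | 1.590 | 37.7% | 0.59 |
| 1 min | 5% | 3.950 | 75.9% | 2.95 |
| 5 min | 1% | 5.550 | 10.8% | 0.55 |
| 5 min | 5% | 7.750 | 38.7% | 2.75 |

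At q = 0, M = m and the problem disappears.

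**How the Kaplan-Meier median behaves.** If all perceivers respond at 10 seconds and q = 5%, the curve falls to 0.05 at 10 seconds and the median is 10 seconds. At q = 45% it falls to 0.45, still below one half, so the median is again 10 seconds, while the imputed mean is 0.55 × 1/6 + 60 × 0.45 = 27.09 min. The median is therefore not pulled by values of 60, but it also says almost nothing about q until more than half feel no cooling, when it is not reached.

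**Location.** A participant who feels cooling only in the mouth is a perceiver if any location counts, and a never-perceiver for nose and throat. So q depends on a definition the plan does not give.

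**The case against.** The other side has several fair points. The numbered rules make the imputed reading fairly clear, so a short clarifying clause would remove most of the doubt. On that reading the error makes onset look later, which is against the sponsor's interest, while the Kaplan-Meier median will usually look more favourable. The median, range and Kaplan-Meier median are reported beside the mean, so a large gap would be visible. Onset is secondary and descriptive in a single-arm study. The large percentage shares arise partly because the base is tiny: at q = 1% the shift is about 0.6 minutes.

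All of this stands as a limit on size. None of it makes 60 minutes a meaningful onset time for someone who felt nothing, and the visible alternatives are not the figure to be claimed. The favourable lean of the median is a real drawback, which is why the never-perceiver percentage has to be part of the claim.

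Two stronger readings are tempting. A reader might infer that the 60-minute rule contradicts Section 10.1 ("Missing data will not be imputed") and Section 11.5 ("Any missing data will be left as such"). For completers it does not, because no sensation is an observed answer. The rules can collide only for someone who leaves before 60 minutes without having marked cooling, which is possible (Section 6.4.2: "A participant may withdraw from the study at any time at his/her own request"). A reader might then apply the table above to such early leavers. The documents do not support rates of that kind: there is one supervised visit of 60-75 minutes (5.1), and dropouts are replaced (6.5). Replacement does not remove a dropout's data from the analysis (10.2), so a rule is useful, but no size can be attached to it.

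**Conclusion.** The point holds for the onset claim. As most naturally read, the plan builds the share who never feel cooling into a figure presented as speed of onset, and biases that figure toward a later time. Every size quoted is conditional on an assumed q and m. The 38-95% range needs both q of 1-5% and a perceivers' mean of 1 minute or less; it is not a forecast, and with a 5-minute mean it falls to 11-39%.

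It would go too far to say that the plan leaves the handling of never-perceivers wholly open, since the text leans clearly to imputation. It would also go too far to say that the study's main conclusion is at risk. The primary variable is agreement on a 5-point scale and uses none of these times.

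**What to change.** In Section 10.3 and the synopsis, replace the onset claim and its never-perceiver rule with wording such as:

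*The onset of cooling will be claimed as the Kaplan-Meier median time to first perceived cooling, always stated together with the percentage of participants who never perceived cooling. Participants who perceive none are censored at their last assessment (60 minutes for completers). The mean with 60 minutes imputed is a sensitivity analysis only.*

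Also:
- State whether onset is for any location, for each location, or both, and give the median and the percentage for each definition used.
- Apply this wording to onset only. State separately how never-perceivers enter the duration claim, so that the 60-minute value is not carried into duration, where it would credit them with the longest possible effect.

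The cost is wording in two places. No new data are needed, and the Kaplan-Meier median is already planned. The downside is that the median is not reached if fewer than half perceive cooling, and otherwise responds little to never-perceivers, so the percentage cannot be dropped from the claim.

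Minimum alternative: keep the mean, state that the 60-minute values enter it, and report the never-perceiver percentage with it. Either choice should be fixed before the data are seen.

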### **10.4 Determination of Sample Size**

The sample size of 400 participants was based on accepted industry standards for sensory studies.

## **11. DATA HANDLING AND QUALITY ASSURANCE**

### **11.1 Data Recording**

The data collection tool for this study will be questionnaires.

## Source Documentation

The site must implement processes to ensure availability of all required source documentation.

It is the expectation of the sponsor that all data entered into the CRF has source documentation available at the site.

It is the expectation of the sponsor that all data entered into the CRF has source documentation available at the site except for the data listed below which will be entered directly into the CRF; thus, these CRF data will be the source and no additional source documentation will be available.

